12.2 LABORATORY PARAMETERS

Each laboratory parameter will be described at baseline, W6, W14, M6, M9 and M12 and presented as follows:

Variable	Visit	Statistics / Modality	Safety Population (N = XX)
Laboratory parameter 1	Baseline	N (N Missing)	XX (XX)
		Mean ± SD	XX.X ± XX.X
		Median [Min ; Max]	XX [XX ; XX]
	W6	Not clinically significant	n/N (XX.X%)
		Clinically significant	n/N (XX.X%)
		Missing	n
	W14	N (N Missing)	XX (XX)
		Mean ± SD	XX.X ± XX.X
		Median [Min ; Max]	XX [XX ; XX]
	M6	Not clinically significant	n/N (XX.X%)
		Clinically significant	n/N (XX.X%)
		Missing	n
	M9	N (N Missing)	XX (XX)
		Mean ± SD	XX.X ± XX.X
		Median [Min ; Max]	XX [XX ; XX]

	Not clinically significant	n/N (XX.X%)
	Clinically significant	n/N (XX.X%)
	Missing	n
	N (N Missing)	XX (XX)
	Mean ± SD	XX.X ± XX.X
	Median [Min ; Max]	XX [XX ; XX]
M12	Not clinically significant	n/N (XX.X%)
	Clinically significant	n/N (XX.X%)
	Missing	n

...

This table will be completed for the following parameters:

- Leucocytes
- Neutrophils
- Lymphocytes
- Monocytes
- Eosinophils
- Hemoglobin
- Platelets
- PR
- aPTT
- Glycaemia
- Creatinine
- Uric acid
- Calcium
- Potassium
- Magnesium
- Total protein

- Albumin
- Total bilirubin
- Alkaline phosphatases
- SGOT (ASAT)
- SGPT (ALAT)
- LDH

12.3 PHYSICAL EXAMINATION

Each body system of the clinical examination will be described at baseline, W6, W14, M6, M9 and M12 and presented as follows:

Variable	Visit	Statistics	Safety Population (N = XX)
Parameter 1	Baseline	N (N Missing)	XX (XX)
		Mean \pm SD	XX.X \pm XX.X
		Median [Min ; Max]	XX [XX ; XX]
	W6	N (N Missing)	XX (XX)
		Mean \pm SD	XX.X \pm XX.X
		Median [Min ; Max]	XX [XX ; XX]
	W14	N (N Missing)	XX (XX)
		Mean \pm SD	XX.X \pm XX.X
		Median [Min ; Max]	XX [XX ; XX]
	M6	N (N Missing)	XX (XX)
		Mean \pm SD	XX.X \pm XX.X
		Median [Min ; Max]	XX [XX ; XX]
	M9	N (N Missing)	XX (XX)
		Mean \pm SD	XX.X \pm XX.X
		Median [Min ; Max]	XX [XX ; XX]
	M12	N (N Missing)	XX (XX)
		Mean \pm SD	XX.X \pm XX.X
		Median [Min ; Max]	XX [XX ; XX]

...

This table will be completed for the following parameters:

- Cardiac frequency
- Systolic arterial pressure
- Diastolic arterial pressure
- Temperature
- O2 saturation

13. DISCUSSION AND OVERALL CONCLUSIONS

At the end of the study evaluation, the principle investigator presents a final report, containing the clinical report, single tables, and the final conclusions. Publication of the results is realized independently from the outcome of the study. The study or parts of the study should be published by the writing committee only which consists of the persons in charge of the study as mentioned on the front page. According to the EBMT rules, co-authors will be offered to the local PI of participating centres, the order depending on the number of patients included by the respective centres, or depending on their contribution to the protocol or the realization of the study. Other investigators will be mentioned in the addendum. All publications and/or communications related to this study should at least mention the PI of the study and the sponsor.

14. TABLES, FIGURES AND GRAPHS

14.1 TABLES

Table Number	Population	Table Title / Summary
14.1 Demographic and Baseline Data		
14.1.1 Disposition and Deviations		
14.1.1.1	All Patients	Study Disposition
14.1.1.2	All Patients	Protocol Deviations
14.1.1.3	All Patients	Analyses Populations
14.1.2 Demographic Data and other baseline characteristics		
14.1.2.1	Safety	Demographic characteristics
14.1.2.2	Safety	Baseline characteristics
14.1.2.3	Safety	Signs and symptoms of cGvHD at baseline
14.1.3 ATO and associated treatments		
14.1.3.1	Safety	Arsenic trioxide therapy
14.1.4.1	Safety	Associated treatment
14.1.4.2	Safety	Concomitant treatments
14.1.4.3	Safety	Secondary immunosuppressive treatment
14.2 Efficacy – Primary criterion		
14.2.1 Main analyses		
14.2.1.1	FAS	Complete or partial response at 6 months (PI response) – Overall
14.2.1.2	FAS	Complete and partial response at 6 months (PI response) – Overall
14.2.1.3	FAS	Complete or partial response at 6 months (PI response) – By sex
14.2.1.4	FAS	Complete and partial response at 6 months (PI response) – By sex
14.2.1.5	FAS	Complete or partial response at 6 months (PI response) – By center
14.2.1.6	FAS	Complete and partial response at 6 months (PI response) – By center
14.2.1.7	FAS	Complete or partial response at 6 months (PI response) – By number of cycles of ATO
14.2.1.8	FAS	Complete and partial response at 6 months (PI response) – By number of cycles of ATO
14.2.1.9	FAS	Complete or partial response at 6 months (PI response) – By use of Ciclosporin or not
14.2.1.10	FAS	Complete and partial response at 6 months (PI response) – By use of Ciclosporin or not
14.2.1.11	FAS	Complete or partial response at 6 months (PI response) – By number of organs involved in cGvHD

Table Number	Population	Table Title / Summary
14.2.1.12	FAS	Complete and partial response at 6 months (PI response) – By number of organs involved in cGvHD
14.2.1.13	FAS	Complete or partial response at 6 months (PI response) – By GvHD severity at baseline
14.2.1.14	FAS	Complete and partial response at 6 months (PI response) – By GvHD severity at baseline
14.2.2 Sensitivity analyses		
14.2.2.1	PP	Complete or partial response at 6 months (PI response) – Overall
14.2.2.2	PP	Complete and partial response at 6 months (PI response) – Overall
14.2.2.3	FAS	Complete or partial response at 6 months (computed response) – Overall
14.2.2.4	FAS	Complete and partial response at 6 months (computed response) – Overall
14.2.2.5	FAS	Complete or partial response at 6 months (computed response) – By sex
14.2.2.6	FAS	Complete and partial response at 6 months (computed response) – By sex
14.2.2.7	FAS	Complete or partial response at 6 months (computed response) – By center
14.2.2.8	FAS	Complete and partial response at 6 months (computed response) – By center
14.2.2.9	FAS	Complete or partial response at 6 months (computed response) – By number of cycles of ATO
14.2.2.10	FAS	Complete and partial response at 6 months (computed response) – By number of cycles of ATO
14.2.2.11	FAS	Complete or partial response at 6 months (computed response) – By use of Ciclosporin or not
14.2.2.12	FAS	Complete and partial response at 6 months (computed response) – By use of Ciclosporin or not
14.2.2.13	FAS	Complete or partial response at 6 months (computed response) – By number of organs involved in cGvHD
14.2.2.14	FAS	Complete and partial response at 6 months (computed response) – By number of organs involved in cGvHD
14.2.2.15	FAS	Complete or partial response at 6 months (computed response) – By GvHD severity at baseline
14.2.2.16	FAS	Complete and partial response at 6 months (computed response) – By GvHD severity at baseline
14.2.2.17	FAS	Complete or partial response at 6 months (PI response) without patients 06-07, 06-08 and 06-09 – Overall
14.2.2.18	FAS	Complete and partial response at 6 months (PI response) without patients 06-07, 06-08 and 06-09 – Overall
14.2.2.19	FAS	Complete or partial response at 6 months (computed response) without patients 06-07, 06-08 and 06-09 – Overall

Table Number	Population	Table Title / Summary
14.2.2.20	FAS	Complete and partial response at 6 months (computed response) without patients 06-07, 06-08 and 06-09 – Overall
14.3 Efficacy – Secondary criteria		
14.3.1 Response at 6 months by organ		
14.3.1	FAS	Response at 6 months by organ
14.3.2	PP	Response at 6 months by organ
14.3.2 Survival analyses		
14.3.2.1a	FAS	Failure free survival at M6
14.3.2.1B	PP	Failure free survival at M6
14.3.2.2a	FAS	Failure free survival at M12
14.3.2.2b	PP	Failure free survival at M12
14.3.2.3a	FAS	Progression free survival at M6
14.3.2.3b	PP	Progression free survival at M6
14.3.2.4a	FAS	Progression free survival at M12
14.3.2.4b	PP	Progression free survival at M12
14.3.2.5a	FAS	Overall survival at M6
14.3.2.5b	PP	Overall survival at M6
14.3.2.6a	FAS	Overall survival at M12
14.3.2.6b	PP	Overall survival at M12
14.3.3 Treatment by corticosteroids		
14.3.3.1	FAS	Treatment by corticosteroids by visit – Absolute values and change from baseline
14.3.4 Quality of life assessment		
14.3.4.1	FAS	FACT-BMT by visit – Absolute values and change from baseline
14.3.4.2	FAS	Lee symptom scale by visit – Absolute values and change from baseline
14.3.5 Assessment of chronic GVHD activity post-ATO treatment		
14.3.5.1	FAS	Global chronic GVHD activity by visit

Table Number	Population	Table Title / Summary
14.3.5.2	FAS	Chronic GVHD activity for each organ by visit
14.3.5.3	FAS	Physician assessment of current overall chronic GVHD severity by visit
14.3.5.4	FAS	Physician evaluations of chronic GVHD changes by visit
14.4 Safety		
14.4.1 Adverse events		
14.4.1.1	Safety	AEs summary – During treatment (Cycle 1 and/or Cycle 2)
14.4.1.2	Safety	AEs summary - After the last infusion of ATO until 6 months after the first infusion of ATO
14.4.1.3	Safety	AEs summary - From 6 to 12 months after the first infusion of ATO
14.4.1.4	Safety	AEs by SOC/PT
14.4.1.5	Safety	SAEs by SOC/PT
14.4.1.6	Safety	AEs leading to death by SOC/PT
14.4.1.7	Safety	AEs leading to withdrawal by SOC/PT
14.4.1.8	Safety	Related AEs by SOC/PT
14.4.2: Laboratory parameters		
14.4.2.1	Safety	Laboratory parameters by visit – Absolute values
14.4.3: Physical examination		
14.4.3.1	Safety	Physical examination by visit – Absolute values

14.2 FIGURES AND GRAPHS

Figure Number	Population	Figure Title / Summary
14.2 Efficacy – Primary criterion		
14.2.1 Main analyses		
14.2.1.1	FAS	Forest plot of Complete and partial response at 6 months (PI response)
14.2.2 Sensitivity analyses		
14.2.2.1	PP	Forest plot of Complete and partial response at 6 months (PI response)

14.2.2.2	FAS	Forest plot of Complete and partial response at 6 months (computed response)
14.2.2.3	FAS	Forest plot of Complete and partial response at 6 months (PI response) without patients 06-07, 06-08 and 06-09
14.2.2.4	FAS	Forest plot of Complete and partial response at 6 months (computed response) without patients 06-07, 06-08 and 06-09
14.3 Efficacy – Secondary criteria		
14.3.1 Survival analyses		
14.3.1.1a	FAS	Kaplan-Meier survival plot of Failure free survival at M6
14.3.1.1b	PP	Kaplan-Meier survival plot of Failure free survival at M6
14.3.1.2a	FAS	Kaplan-Meier survival plot of Failure free survival at M12
14.3.1.2b	PP	Kaplan-Meier survival plot of Failure free survival at M12
14.3.1.3a	FAS	Kaplan-Meier survival plot of Progression free survival at M6
14.3.1.3b	PP	Kaplan-Meier survival plot of Progression free survival at M6
14.3.1.4a	FAS	Kaplan-Meier survival plot of Progression free survival at M12
14.3.1.4b	PP	Kaplan-Meier survival plot of Progression free survival at M12
14.3.1.5a	FAS	Kaplan-Meier survival plot of Overall survival at M6
14.3.1.5b	PP	Kaplan-Meier survival plot of Overall survival at M6
14.3.1.6a	FAS	Kaplan-Meier survival plot of Overall survival at M12
14.3.1.6b	PP	Kaplan-Meier survival plot of Overall survival at M12
14.3.2 Treatment by corticosteroids		
14.3.2.1	FAS	Stacked bars of Prednisone dose by visit
14.3.2.2	FAS	Stacked bars of change from baseline of Prednisone dose by visit
14.3.3 Quality of life assessment		
14.3.3.1.1a	FAS	Boxplot of FACT-BMT Physical well-being subscore by visit
14.3.3.1.1b	FAS	Boxplot of change from baseline of FACT-BMT Physical well-being subscore by visit
14.3.3.1.2a	FAS	Boxplot of FACT-BMT Social/Family well-being subscore by visit
14.3.3.1.2b	FAS	Boxplot of change from baseline of FACT-BMT Social/Family well-being subscore by visit

14.3.3.1.3a	FAS	Boxplot of FACT-BMT Emotional subscore by visit
14.3.3.1.3b	FAS	Boxplot of change from baseline of FACT-BMT Emotional well-being subscore by visit
14.3.3.1.4a	FAS	Boxplot of FACT-BMT Functionnal subscore by visit
14.3.3.1.4b	FAS	Boxplot of change from baseline of FACT-BMT Functionnal subscore by visit
14.3.3.1.5a	FAS	Boxplot of FACT-BMT Other concerns subscore by visit
14.3.3.1.5b	FAS	Boxplot of change from baseline of FACT-BMT Other concerns subscore by visit
14.3.3.1.6a	FAS	Boxplot of global FACT-BMT score by visit
14.3.3.1.6b	FAS	Boxplot of change from baseline of global FACT-BMT score by visit
14.3.3.2.1a	FAS	Boxplot of Lee symptom scale skin subscore by visit
14.3.3.2.1b	FAS	Boxplot of change from baseline of Lee symptom scale skin subscore by visit
14.3.3.2.2a	FAS	Boxplot of Lee symptom scale eyes and mouth subscore by visit
14.3.3.2.2b	FAS	Boxplot of change from baseline of Lee symptom scale eyes and mouth subscore by visit
14.3.3.2.3a	FAS	Boxplot of Lee symptom scale breathing subscore by visit
14.3.3.2.3b	FAS	Boxplot of change from baseline of Lee symptom scale breathing subscore by visit
14.3.3.2.4a	FAS	Boxplot of Lee symptom scale eating and digestion subscore by visit
14.3.3.2.4b	FAS	Boxplot of change from baseline of Lee symptom scale eating and digestion subscore by visit
14.3.3.2.5a	FAS	Boxplot of Lee symptom scale energy subscore by visit
14.3.3.2.5b	FAS	Boxplot of change from baseline of Lee symptom scale energy subscore by visit
14.3.3.2.6a	FAS	Boxplot of Lee symptom scale mental and emotional subscore by visit
14.3.3.2.6b	FAS	Boxplot of change from baseline of Lee symptom scale mental and emotional subscore by visit
14.3.3.2.7a	FAS	Boxplot of Global Lee symptom scale subscore by visit
14.3.3.2.7b	FAS	Boxplot of change from baseline of Global Lee symptom scale subscore by visit
14.3.4 Assessment of chronic GVHD activity post-ATO treatment		
14.3.4.1	FAS	Stacked bars of Global chronic GVHD activity by visit

14.3.4.2	FAS	Stacked bars of Chronic GVHD activity for each organ by visit
14.3.4.3	FAS	Boxplot of total bilirubin by visit
14.3.4.4	FAS	Boxplot of ALT (SGPT) by visit
14.3.4.5	FAS	Boxplot of PAL (ALK) by visit
14.3.4.6	FAS	Boxplot of FEV1 by visit
14.3.4.7	FAS	Boxplots of Physician assessment of current overall chronic GVHD severity by visit
14.3.4.8	FAS	Boxplots of Physician evaluations of chronic GVHD changes by visit

16. LISTINGS

Listing Number	Listing Title / Summary
16.2.1 Discontinued patients	
16.2.1.1	Study Completion
16.2.1.2	Visits and Dates of Visits
16.2.2 Protocol Deviations	
16.2.2.1	Protocol Deviations
16.2.3 Patients Excluded from the Efficacy Analysis	
16.2.3.1	Subject Eligibility
16.2.3.2	Populations
16.2.4 Demographic Data	
16.2.4.1	Demographic characteristics
16.2.4.2	History of GvHD
16.2.4.3	GvHD prophylaxis
16.2.4.4	Diagnostic of chronic GvHD
16.2.4.5	Ciclosporin therapy
16.2.4.6	Prednisone therapy
16.2.4.7	Concomitant treatments
16.2.5 Efficacy Response Data	
16.2.5.1	Clinical assessment at each visit
16.2.5.2	Scores with abnormalities present but explained entirely by non-GVHD documented cause at each visit
16.2.5.3	GvHD Chronic form A at each visit
16.2.5.4	Response at each visit
16.2.6 Efficacy Response Data	
16.2.6.1	All Adverse Events
16.2.6.2	Laboratory results
16.2.6.3	Physical examination

17. APPENDICES

17.1 RESPONSE CALCULATION ALGORITHM

Etude GMED_16_001 : Evaluation des réponses complètes et partielles – 19/10/2020

Les réponses sont définies comme (règles de calcul basées sur le protocole et l'article Lee et al)

- Complete response at a visit: Lorsque tous les scores de « cGVHD activity assessment form A » des organes suivants sont à 0 ou que la variable "abnormalities present but explained entirely by non-GVHD documented cause » soit égale à Oui.

Détails :

Si une valeur est manquante pour un des organes atteints lors de la visite V1, la réponse ne peut pas être considérée comme complète. le fait que la valeur est manquante sera documentée.

Si une valeur à la visite d'intérêt est manquante sur un organe non atteint lors de la visite V1, la réponse complète peut être établie, car les réponses complètes ou partielles ne sont établies que sur les organes atteints à V1.

Si « abnormalities present but explained entirely by non-GVHD documented cause » = Oui pour un organe à la visite considérée, le score de cet organe n'est pas corrigé et cet organe n'est pas considéré pour l'évaluation de la réponse complète. cela ne créera pas de valeur manquante pour cet organe et n'empêchera pas la réponse d'être considérée comme complète si les informations sur les autres organes sont disponibles.

- BSA=0 ET skin features=0

M6_GVHD_A_S (préfixe M6 ou C1W6, W14, M9 et M12 selon la visite considérée)

M6_GVHD_A_S_F_S

M6_GVHD_A_S_ABN

- Eyes=0

M6_GVHD_A_E

M6_GVHD_A_E_ABN

- Gastrointestinal=0 (pour chacun des 3 scores : Gastro-oesophageal, Gastro-upper, Gastro-lower)

M6_GVHD_A_GASTRO1

M6_GVHD_A_GASTRO2

M6_GVHD_A_GASTRO3

M6_GVHD_GAST_ABN

- Mouth=0 (considérer la somme des 3 scores : Erythema, Lichenoid, Ulcers)

M6_GVHD_A_MOUTH1
 M6_GVHD_A_MOUTH2
 M6_GVHD_A_MOUTH3
 M6_GVHD_MTH_ABN

Joint and fascia =0

M6_GVHD_A_J
 M6_GVHD_A_J_ABN

Liver : les 3 valeurs (Bilirubine, ALAT et PAL) sont en dessous des ULN (Unité limite supérieure) si le score hépatique était >0 à V1 (table 1 et annexe du protocole)

.<M6_GVHD_A_L_SGPT_V<=M6_GVHD_A_L_SGPT_U_V
 .<M6_GVHD_A_L_ALK_V<=M6_GVHD_A_L_ALK_U_V
 M6_GVHD_LIV_ABN

Le score à V1 est calculé comme :

Score = 0 : Bilirubine normale WITH ALAT AND PAL < 3 UNL

(.<V1_GVHD_A_L_BILI_V<=V1_GVHD_A_L_BILI_U_V et
 .<V1_GVHD_A_L_SGPT_V<3* V1_GVHD_A_L_SGPT_U_V et
 .<V1_GVHD_A_L_ALK_V<3* V1_GVHD_A_L_ALK_U_V)

Score = 1 : Bilirubine normale WITH 3 UNL<=ALAT < 5 UNL AND 3 UNL <=PAL<5 UNL

Score = 2 : Bilirubine élevée (>1*ULN) mais <= à 3 mg/dL OR ALAT >= 5 UNL OR PAL >=5 UNL (non mentionné dans article NIH).

Score = 3 : Bilirubine élevée > à 3 mg/dL

Lung : si FEV1 >=80% et FEV1<70 à V1. et dans le cas où la valeur de FEV1 est manquante, si le score est égal à 0

M6_GVHD_A_LU_FEV1_V>= 80
 missing(M6_GVHD_A_LU_FEV1_V) and M6_GVHD_A_L=0
 M6_GVHD_A_L
 M6_GVHD_A_L_ABN

Calcul de réponse par organe :

Aucun calcul de réponse **par organe** (complète, partielle ou progression) n'est effectué si :

- « abnormalities present but explained entirely by non-GVHD documented cause » = Oui pour un organe à la visite considérée
- CR_*organe*, PR_*organe* et PD_*organe* sont alors mis à . (manquant)

Aucun calcul de réponse complète ou partielle **par organe** n'est effectué si :

- l'organe n'est pas atteint à V1 ou abnormalities present but explained entirely by non-GVHD documented cause » = Oui pour un organe à la visite V1.
- la progression est recherchée même si pas d'atteinte à V1
- CR_*organe* et PR_*organe* sont alors mis à . (manquant)

- **Partial response by organ:** en se basant sur les mêmes scores et en s'intéressant aux diminutions (ou augmentations) entre V1 (mêmes variables qu'indiquées précédemment mais qui commencent par « V1 » au lieu de « M6 ») et la visite considérée (M6, W6, W14, M9 ou M12)

- une diminution d'1 point pour les scores sur des échelles de 0 à 4 pour : Skin BSA, Skin features, Eyes, Joints, Gastro-oesophageal, Gastro-upper, Gastro-lower,
- une diminution de 2 points pour la somme des 3 sous-scores pour Mouth
- pour Lung, une augmentation entre V1 et la visite d'au moins 10% sur FEV1 avec FEV1 à V1 <70. Dans le cas de FEV1 manquants à V1 et ou M6, une diminution d'1 point sur le score 'lungs'
- pour Liver, (Bilirubine, ALAT ou PAL),
- si les valeurs à M6 sont en dessous des normales, la réponse est considérée Complète
- sinon la recherche d'une réponse partielle est effectuée : diminution de 50% de la valeur initiale
 Le ratio est calculé ainsi : $(M6-V1/V1)*100$ et si le ratio est inférieur à -50 (mais pas de progression pour une des autres valeurs), il y a une réponse partielle

Global Partial response: au moins une réponse partielle sur un organe et avec une absence de progression pour un autre site

- **Progressive disease by organ:**

- peau, yeux, œsophage, tractus gastro-intestinal supérieur et inférieur : augmentation 1 point ou plus sur échelle de 0 à 3 = progression SAUF si changement de 0 à 1 (progression non spécifique)
- Joint: augmentation d'1 point ou plus = progression
- bouche : changement de 2 points ou plus sur la somme des 3 sous-scores

- pour Lung, diminution de 10 % avec FEV1 à V1 < 75% . Dans le cas de FEV1 manquants, augmentation d'1 point ou plus *SAUF* si changement de 0 à 1 (progression non spécifique)

- pour Liver, si l'une des valeurs à M6 est au-dessus de la normale pour Bilirubine, ALAT ou PAL, la recherche d'une progression est effectuée : la différence M6 – V1 est calculée et si la différence est supérieure à 2*ULN, il y a Progression.

Global progressive disease : si au moins un site avec une progression

Mixed response: si **Progressive disease** sur au moins un organe et **Partial response** sur au moins un autre

Extraits du protocole :

Table 4. Response determination for chronic GvHD (extrait du protocole)

Organ	Complete Response	Partial Response	Progression
Skin	NIH Skin Score 0 after previous involvement	Decrease in NIH Skin Score by 1 or more points	Increase in NIH Skin Score by 1 or more points, except 0 to 1
Eyes	NIH Eye Score 0 after previous involvement	Decrease in NIH Eye Score by 1 or more points	Increase in NIH Eye Score by 1 or more points, except 0 to 1
Mouth	NIH Modified OMRS 0 after previous involvement	Decrease in NIH Modified OMRS of 2 or more points	Increase in NIH Modified OMRS of 2 or more points
Esophagus	NIH Esophagus Score 0 after previous involvement	Decrease in NIH Esophagus Score by 1 or more points	Increase in NIH Esophagus Score by 1 or more points, except 0 to 1
Upper GI	NIH Upper GI Score 0 after previous involvement	Decrease in NIH Upper GI Score by 1 or more points	Increase in NIH Upper GI Score by 1 or more points, except 0 to 1
Lower GI	NIH Lower GI Score 0 after previous involvement	Decrease in NIH Lower GI Score by 1 or more points	Increase in NIH Lower GI Score by 1 or more points, except from 0 to 1
Liver	Normal ALT, alkaline phosphatase, and Total bilirubin after previous elevation of 1 or more	Decrease by 50%	Increase by 2 × ULN
Lungs	- Normal %FEV1 after previous involvement - If PFTs not available, NIH Lung Symptom Score 0 after previous involvement	- Increase by 10% predicted absolute value of %FEV1 - If PFTs not available, decrease in NIH Lung Symptom Score by 1 or more points	- Decrease by 10% predicted absolute value of %FEV1 - If PFTs not available, increase in NIH Lung Symptom Score by 1 or more points, except 0 to 1
Joints and fascia	Both NIH Joint and Fascia Score 0 and P-ROM score 25 after previous involvement by at least 1 measure	Decrease in NIH Joint and Fascia Score by 1 or more points or increase in P-ROM score by 1 point for any site	Increase in NIH Joint and Fascia Score by 1 or more points or decrease in P-ROM score by 1 point for any site
Global	Clinician overall severity score 0	Clinician overall severity score decreases by 2 or more points on a 0-10 scale	Clinician overall severity score increases by 2 or more points on a 0-10 scale

ULN indicates upper limit of normal.

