  - For joint/fascia, a worsening of 1 point or more on the 0 to 3 scale is considered progression, even if from 0 to 1, because a change to score 1 was considered meaningful progression that would prompt a change in therapy. For joints assessed by the photographic range of motion, a worsening of 1 or more points for the 7-point scales and 1 or more points for the 4-point scale is considered progression.
  - For mouth, a worsening of 2 or more points on the 1-point scale indicates

progression.

- Worsening of liver GvHD is defined by an increase of 2 or more times the upper limit of normal for the assay for alanine transaminase, alkaline phosphatase, or total bilirubin.
- For patients with lung involvement, absolute worsening of FEV1 by 10% predicted or more (eg, 50% to 40%) is considered progression, as long as the final %FEV1 is < 65% (because initial %FEV1 must be < 75% to establish the diagnosis of lung involvement). If PFTs are not available, then worsening of the clinical lung score based on symptoms by 1 or more points should be scored as progression, except from score 0 to 1, which is considered trivial progression because of its lack of specificity for lung chronic GvHD.
- Mixed response is defined as CR or PR in at least one organ accompanied by progression in another organ
- Unchanged: outcome that do not meet criteria for CR, PR, PF or mixed response are considered unchanged

Response determination for chronic GvHD is indicated in the table below:

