- For joint and fascia, scoring from 0 to 3 is based on symptoms. The P-ROM score is an exploratory measure that could be very useful in that exploration.
- For mouth, scoring from 0 to 12 is based on symptoms.
- For gastrointestinal tract, scoring from 0 to 3 is performed for the upper and lower gastrointestinal tract and esophagus. In addition patient weight must be recorded.
- For liver, total serum bilirubin, alkaline phosphatase and alanine aminotransferase must be recorded.
- Genital tract requires a specialist exam and measure of genital response are considered exploratory. Therefore, genital tract is not included in evaluation of chronic GvHD response.

Abnormality present but explained entirely by non-chronic GvHD documented cause must be specified and the organ will not be considered as involved for evaluation of chronic GvHD response.

In addition, physician should provide a subjective assessment of current overall chronic GvHD severity on a 4-points scale (no chronic GvHD, mild, moderate or severe) without knowledge of the calculated NIH global severity score. They should also provide an assessment of current overall chronic GvHD severity on a 11-point numerical scale (0 indicates no GvHD manifestation; 10 indicates most severe chronic GvHD symptoms possible). Clinicians should also provide their evaluations of chronic GvHD changes since the last assessment scored on a 7-point scale (very much better, moderately better, a little better, about the same, a little worse, moderately worse, very much worse). These semi-quantitative assessments may detect qualitative improvements that are clinically meaningful but not well captured using other measures.

➤ **Patient reported outcome**

Patient reported outcome included chronic GvHD-specific core measure with the chronic GvHD activity assessment-patient self-report (Lee Symptom Scale: LSS - Form B) and chronic GvHD non-specific ancillary measure with the FACT-BMT. Patients reported outcome are exploratory and will not be used for decision making response evaluation.

- Organ sites considered in the chronic GvHD activity assessment-patient self-report included skin and joint, mouth, genital tract and eyes. In addition, similarly to clinician assessed chronic GvHD, at each assessment, patients should score their perceptions of overall chronic GvHD severity, overall severity of symptoms, and change in symptom severity compared with the last assessment, using the same response options used by clinicians.

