Joint and fascia	Both NIH Joint and Fascia Score 0 and P-ROM score 25 after previous involvement by at least 1 measure	Decrease in NIH Joint and Fascia Score by 1 or more points or increase in P-ROM score by 1 point for any site	Increase in NIH Joint and Fascia Score by 1 or more points or decrease in P-ROM score by 1 point for any site
Global	Clinician overall severity score 0	Clinician overall severity score decreases by 2 or more points on a 0-10 scale	Clinician overall severity score increases by 2 or more points on a 0-10 scale

ULN indicates upper limit of normal.

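### The SAP endpoint table uses P-ROM for joint/fascia CR, PR and progression, but the SAP 17.1 algorithm uses only the 0-3 joint score, so the computed response and progression can contradict the table

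*SAP*

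**What the plan says.** The response table in SAP 8.2.1 gives P-ROM a role in all three joint/fascia categories:

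- CR: "Both NIH Joint and Fascia Score 0 and P-ROM score 25 after previous involvement by at least 1 measure"
- PR: "Decrease in NIH Joint and Fascia Score by 1 or more points or increase in P-ROM score by 1 point for any site"
- Progression: "Increase in NIH Joint and Fascia Score by 1 or more points or decrease in P-ROM score by 1 point for any site"

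Protocol Table 4 has the same row, and SAP 17.1 reprints it directly after its algorithm. The response text in Protocol 7.3.2.1, repeated in 9.3, also treats P-ROM loss as progression: "For joints assessed by the photographic range of motion, a worsening of 1 or more points for the 7-point scales". That sentence goes on to set the same threshold for the 4-point scale.

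The algorithm in SAP 17.1 says that it rests on the protocol, but it names only the joint score variable and its flag for a non-GvHD cause:

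- CR: "Joint and fascia =0"
- PR: "une diminution d'1 point pour les scores sur des échelles de 0 à 4 pour : Skin BSA, Skin features, Eyes, Joints"
- Progression: "Joint: augmentation d'1 point ou plus = progression"

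No P-ROM variable or rule appears in it, and no reason is given. (It describes the PR scales as 0 to 4, whereas the forms score joints 0 to 3.)

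Protocol 9.2 adds: "The P-ROM score is an exploratory measure that could be very useful in that exploration". Protocol 7.1.2 keeps P-ROM out of the global severity calculation.

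**The concern.** The SAP holds two joint rules. The endpoint table applies one and the program that computes response applies the other. The joint score is coarse: the description of score 1 in Protocol Appendix 2 fits both normal and slightly reduced movement, so movement can change while the score stays put. Where that happens, the two rules can give the same patient different organ responses, different global responses and a different progression status.

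This matters most for the purpose of the computed response. The trial is single-arm and unblinded, and sensitivity analyses b and d in SAP 11.4.1.2 set a rule-based response against the investigator's judgement. If the rule departs from the endpoint table, a disagreement between the two cannot be interpreted, because it may reflect only the missing P-ROM component. The organ-response table (SAP 11.4.2.1) and PFS (SAP 11.4.2.2 b) use the algorithm directly.

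**Working it through.** **The plan's own figure.** Protocol 10.7 requires 17 or more successes in 21 patients, with P0 = 60%, P1 = 85%, alpha 0.05 and beta 0.20. The exact binomial gives P(X ≥ 17 | n = 21, p = 0.60) = 0.0370 and P(X ≥ 17 | n = 21, p = 0.85) = 0.8025. With 10% dropout, 21/0.90 = 23.3, rounded up to 24. The design reproduces, and 21 and 24 serve below as illustrative denominators.

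**Resolution of the two measures.** From Protocol Appendix 2, shoulder, elbow and wrist/finger are scored 1-7 and the ankle 1-4. Maximum: 7 + 7 + 7 + 4 = 25. Minimum: 1 + 1 + 1 + 1 = 4. Range: 25 − 4 = 21 one-point steps (22 levels). The joint score has 3 steps (4 levels).

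**The two rules side by side.** The pairs are invented for illustration. P-ROM is the total, and all site changes within a case are taken to go in the same direction.

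| Joint score, V1→M6 | P-ROM, V1→M6 | SAP 17.1 algorithm | SAP 8.2.1 table |
|---|---|---|---|
| 1→1 | 20→18 | unchanged | progression |
| 0→0 | 25→23 | not involved, no progression | progression |
| 2→0 | 20→23 | CR | PR (P-ROM not 25) |
| 1→1 | 20→22 | unchanged | PR |
| 1→0 | 22→20 | CR | better on score, progression on P-ROM |
| 0→0 | 22→22 | not involved | involved on P-ROM, unchanged |

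**Effect on the global result.**

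1. *P-ROM loss, joint score unchanged, PR in another organ (say skin).* Under 17.1 there is an organ PR and no progression elsewhere, so the patient is a global PR. Under 8.2.1 progression in the joint bars PR; Protocol 9.3 calls this a mixed response. A non-responder becomes a computed responder, and a progression event disappears. One point is enough: a wrist going from 6 to 5 with the other sites full takes the total from 7 + 7 + 6 + 4 = 24 to 7 + 7 + 5 + 4 = 23.
2. *Joint score falls to 0, P-ROM stays below 25 without loss.* 17.1 gives joint CR. 8.2.1 gives joint PR, because the score fell by at least 1. With no progression elsewhere the patient counts in CR+PR under both rules.
3. *P-ROM gain as the only improvement.* Under 8.2.1 this is PR if nothing progressed. Under 17.1 the patient is not a responder.

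Case 1 raises the computed CR+PR rate, case 3 lowers it and case 2 leaves it alone.

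**Size per patient.** 1/24 = 4.2 and 1/21 = 4.8 percentage points of the computed rate. The documents do not say how many patients have joint disease, so no total effect follows.

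**The case against.** **The main analysis does not use the algorithm.** SAP 11.4.1.1 takes the investigator's judgement at M6. This stands. A reader might infer that the primary result is inflated; the documents do not support that, and an upward bias is not established even for the computed rate, since P-ROM-only gains are missed too.

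**Residual restriction does not create responders.** This also stands. It would be tempting to say that a patient left with restricted joints is wrongly counted as a responder, but after a joint-score fall 8.2.1 itself grants PR. Only P-ROM worsening without a joint-score rise can turn a non-responder into a responder. Where the score rises as well, both rules call progression. Where the joint is the only improving organ and its two measures disagree, the table does not settle the outcome, because PR is barred by progression at another site.

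**P-ROM is exploratory.** Protocol 9.2 gives the algorithm some support. It does not resolve the conflict: Protocol 7.1.2 excludes P-ROM only from global severity, and 9.2 does not exclude it from response, although the same section does so expressly for the genital tract.

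**P-ROM may not have been collected at follow-up.** The algorithm works on Form A, whose readable joint item (Protocol Appendix 8) is only the 0-3 score. The P-ROM fields are in Appendix 2, and Protocol Table 2 schedules diagnosis and scoring only at selection. Against this, Protocol 9.2 points to Appendix 2 for Form A, and some figures cannot be seen in the copy reviewed. The question stays open, so it would go too far to say that adding P-ROM is the only correct remedy.

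**The PFS consequence is conditional.** SAP 8.2.2 defines PFS by the original disease, whereas 11.4.2.2 b uses chronic GvHD progression from 17.1. P-ROM matters for PFS only under the latter.

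**Conclusion.** The conflict is real and unexplained: following SAP 17.1 can produce computed responses and progression events that contradict the SAP's own endpoint table. It affects sensitivity analyses b and d, the organ-response table and PFS as derived in 11.4.2.2 b. The investigator-judged main analysis is not directly changed.

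The net direction and total size are unknown, because the number of patients with joint disease and the availability of P-ROM after baseline are not given. The 4.2 to 4.8 points per patient assume a denominator of 24 or 21; the FAS in SAP 11.1 may be smaller. The plan should be corrected, but the point does not by itself threaten the primary conclusion.

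**What to change.** Before database lock, reconcile the passages so that one joint rule applies throughout. Either option does this:

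- **(a) Use P-ROM.** Code the 8.2.1 joint rule in 17.1 for patients with P-ROM recorded at both V1 and the visit. Use the joint score for the others, flag them and report their number.
- **(b) Leave P-ROM out.** If it is meant to be exploratory only, or was not collected at follow-up, say so and remove it from the 8.2.1 table, its reprint in 17.1, Protocol Table 4 and the response text in Protocol 7.3.2.1 and 9.3.

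The sponsor should first establish whether P-ROM was recorded at follow-up, since that decides whether (a) is feasible. The cost is a few lines of code or wording. Some computed responses may change, and under (a) patients without P-ROM are classified on the joint score alone, so two rules coexist in the computed data; the flag and count make this visible.
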